## Urinalysis

All subjects must undergo urinalysis testing (leukocyte esterase, blood, pH, and specific gravity [microscopic tests to be completed if dipstick urinalysis is abnormal]) at Screening and Baseline to assess protocol eligibility. Urinalysis testing will be performed thereafter as specified in the [Appendix A](#) Schedule of Assessments and Procedures.

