WBC Decrease – cell/mm 	2,500– 3,999	1,500 – 2,499	< 1,500
WBC Decrease – cell/mm  (African American Males)	2,200 – 2,499	1,200 – 2,199	<1,200
WBC Decrease – cell/mm  (African American Females)	2,200 – 2,499	1,500 – 2,199	<1,500
Neutrophils Decrease – cell/mm 	1,300 – <1,699	1,000 – 1,299	< 1,000
Neutrophils Decrease – cell/mm  (African American Males)	1,000 – 1,299	800 - 999	<800
Neutrophils Decrease – cell/mm  (African American Females)	1,100 – 1,299	1,000 – 1,099	<1,000
Platelets Decreased - cell/mm 	120,000 – <150,000	100,000 – 119,999	<100,000
PT (prothrombin time) – seconds	11.6 – 12.6	12.7 – 13.7	>13.7
PT INR (Prothrombin INR)	1.2-1.4	1.5-1.9	2.0 or higher
PTT (partial thromboplastin time) –seconds	30.1 – 36.8	36.9 – 43.6	>43.6
Total Protein – g/dL	5.5 - 5.9	5.0 - 5.4	<5.0
Alkaline phosphatase – IU/L (Male)	1.1 - ≤ 2.0 x ULN	>2.0 - ≤ 3.0 x ULN	>3.0 x ULN or higher
Alkaline phosphatase – IU/L (Female)	1.1 - ≤ 2.0 x ULN	>2.0 - ≤ 3.0 x ULN	>3.0 x ULN or higher
Hematocrit (Male) - %	33.0 -36.1	29.8 - 32.9	< 29.8
Hematocrit (Female) - %	29.5 - 32.6	26.0 – 29.4	< 26.0
RBC (Male) – x 10  /uL	3.9 - 4.1	3.4 - 3.8	< 3.4

Adverse Events*	Mild (Grade 1)	Moderate (Grade 2)	Severe (Grade 3)
RBC (Female) – x 10  /uL	3.5 - 3.7	3.0 - 3.4	< 3.0
Lymphocytes - cell/mm  decrease	600- 799	500 – 599	< 500
Monocytes – cell/mm  increase	1001-2000	2001-3000	>3000
Eosinophils - cell/mm  increase	871 - 950	951 - 1700	>1700
Basophils - cell/mm  increase	101 - 300	301 - 800	> 800
High Density Lipoproteins (HDL) Male – mg/dL	N/A	N/A	N/A
High Density Lipoproteins (HDL) Female – mg/dL	N/A	N/A	N/A
Total Carbon Dioxide – mEq/L	N/A	N/A	N/A
Total Cholesterol – mg/dL	N/A	N/A	N/A
Low Density Lipoprotein Cholesterol, Direct – mg/dL	N/A	N/A	N/A
Triglycerides – mg/dL	N/A	N/A	N/A
Laboratory Adverse Events* (Urine)			
Protein	1+	2+	>2+
Glucose	1+	2+	>2+
Blood (microscopic) - red blood cells per high power field (rbc/hpf)**	3-10**	11-50**	>50 and/or gross blood**

\*Abnormal laboratory values, performed as part of hematology, chemistry panel, or urinalysis but not listed in Appendix B, VT-1598 TOXICITY GRADING CRITERIA FOR NORMAL HUMAN SUBJECTS, will be evaluated by the study clinicians, recorded in the source document and, if clinically significant, considered AEs and graded according to the criterion described in [Section 8.1](#).

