- UA parameters: specific gravity by dipstick, pH by dipstick, occult blood by dipstick, leukocyte esterase by dipstick. If dipstick urinalysis testing is abnormal, RBC by complete UA and WBC by complete UA will be assessed. Urinalysis WBC count will be measured but the results will not be graded for toxicity.
- VS parameters:
 - VS will be obtained after subjects have rested for at least 5 minutes.
 - VS parameters will be graded according to the toxicity grading criteria in [Table 6](#).
 - Subjects with a history of sinus bradycardia will only have AEs of moderate severity or greater entered for bradycardia/decreased heart rate.
 - The following parameters will be measured:
 - Systolic blood pressure, diastolic blood pressure, pulse, respiratory rate, and temperature.
- ECG parameters:
 - ECG measurements will be conducted in triplicate, and the mean of triplicate values will be used for analysis, including analyses of change from baseline.
 - All ECG triplicate readings will be conducted at least 1 minute apart within a 15-minute period.
 - ECG results will be read by the study PI or a designated clinician and graded according to the toxicity grading criteria in [Table 6](#). For each timepoint, overall interpretation of the ECG will be reported as Normal; Abnormal, Not Interpretable; or Abnormal, Clinically Significant (CS). Evaluation of rhythm, arrhythmia, conduction disturbance, axis, myocardial infarction, ST segment, and other abnormal findings will also be assessed.
 - If QTcF prolongation occurs after dosing then telemetry monitoring will start, and triplicate 12-lead ECGs will be captured every 30 minutes until the average for the triplicates has returned to within 60 ms of the baseline value.
 - The following parameters will be measured:
 - PR interval, QRS duration, QT interval, QTcF interval, RR interval, and mean ventricular heart rate.
 - Prior to 16NOV2020 QTc interval was included in the ECG parameters measured. Because QTc and QTcF are similar intervals, the study team determined that QTc should be removed from the eCRF so as to reduce redundant data collection. QTcF was kept as the interval as it is the parameter referenced in the Inclusion and Exclusion criteria.
- Physical exams:
 - Complete physical exams include the following parameters:

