6. GENERAL STATISTICAL CONSIDERATIONS

6.1. General Principles

Summary statistics for continuous data will include the number of subjects included in analysis (N), mean, standard deviation (SD), median, minimum value (min), and maximum value (max). Summary statistics for discrete data will include frequencies and proportions and may include confidence intervals (CIs) for the proportion. When 95% CIs are given for a proportion, exact (Clopper-Pearson) CIs will be used, unless otherwise specified. All randomized subjects will be included in the summaries of subject demographics. The Safety Population will be used for summaries of safety endpoints and the PK Analysis Population or the PK Analysis Subset will be used for summaries of PK endpoints.

Denominators for safety endpoints will be the number of subjects in the Safety Population. Denominators for clinical laboratory, VS, and ECG results at planned study timepoints will be the number of subjects with available results at the specified timepoint for that parameter. Denominators for the conceptual “Maximum Severity Post Baseline” timepoint for clinical laboratory, VS, and ECG results will be the number of subjects with an observed result for the parameter obtained post dose.

The sort order for listings is indicated in the implementation note for each listing shell ([Appendix 3](#)). The sort order of clinical laboratory tests, VS, and ECG parameters is described in Section [9](#).

All safety and PK analyses will be performed by Dose Group as described in Section [3.3.2](#).

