N=Number of subjects in the Safety Population with the laboratory result assessed at the respective timepoint. Results from subjects in Cohort 3 that continued on to Cohort 6 are counted separately for each study part in both the Any Dose Group and the Placebo Dose Group.

Table 29: Chemistry Summary Statistics Change from Baseline by Parameter, Dose Group, and Timepoint

[Implementation Note: Subjects who received VT-1598 in both Cohorts 3 and 6 will be included separately for each dosing period in the Any Dose Group. Similarly, subjects who received placebo in both Cohorts 3 and 6 will be included separately for each dosing period in the Placebo Dose Group.]

Mean, SD, and median will be reported to one decimal place greater than the original data. Min and max values will be reported with the same number of decimal places as the original data.

Parameter order: albumin, glucose, blood urea nitrogen, potassium, calcium, sodium, chloride, total protein, creatinine, triglycerides, total cholesterol, low-density lipoprotein, high-density lipoprotein, total carbon dioxide, creatine phosphokinase, phosphorus, alkaline phosphatase, aspartate aminotransferase, alanine aminotransferase, total bilirubin, direct bilirubin, magnesium, gamma-glutamyl transferase (GGT), serum cortisol]

Dose Group	Timepoint	N	Change from Baseline			
			Mean	SD	Median	Min, Max
Albumin (g/dL)						
Any Dose	Day 4	x	x	x	x	x, x
	Day 7	x	x	x	x	x, x
	Day 14	x	x	x	x	x, x
	Day 21	x	x	x	x	x, x
40 mg Fasted	Day 4	x	x	x	x	x, x
	...	x	x	x	x	x, x
80 mg Fasted	Day 4	x	x	x	x	x, x
	...	x	x	x	x	x, x
160 mg Fasted	Day 4	x	x	x	x	x, x
	...	x	x	x	x	x, x
160 mg Fed	Day 4	x	x	x	x	x, x
	...	x	x	x	x	x, x
320 mg Fasted	Day 4	x	x	x	x	x, x
	...	x	x	x	x	x, x
640 mg Fasted	Day 4	x	x	x	x	x, x
	...	x	x	x	x	x, x
Placebo	Day 4	x	x	x	x	x, x
	...	x	x	x	x	x, x
Glucose (mg/dL)						
Any Dose	Day 4	x	x	x	x	x, x
...	...	x	x (x)	x (x)	x (x)	x (x)
...						

Notes: N=Number of subjects in the Safety Population with the laboratory result assessed at the respective timepoint. Results from subjects in Cohort 3 that continued on to Cohort 6 are counted separately for each study part in both the Any Dose Group and the Placebo Dose Group.

14.3.5.2 Hematology Results**Table 30: Hematology Abnormal Results by Parameter, Dose Group, and Timepoint**

[Parameter order: hemoglobin, hematocrit, lymphocytes, neutrophils, monocytes, eosinophils, basophils, platelet, red blood cell count, white blood cell count]

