This table will repeat Table 27 for Hematology Parameters

Table 31: Hematology Laboratory Toxicity Grade by Parameter, Dose Group, Timepoint, and Severity

[Parameter order: hemoglobin, hematocrit, lymphocytes, neutrophils, monocytes, eosinophils, basophils, platelet, red blood cell count, white blood cell count.]

This table will repeat Table 28 for Hematology Parameters

Table 32: Hematology Summary Statistics Change from Baseline by Parameter, Dose Group, and Timepoint

[Parameter order: hemoglobin, hematocrit, lymphocytes, neutrophils, monocytes, eosinophils, basophils, platelet, red blood cell count, white blood cell count.]

This table will repeat Table 29 for Hematology Parameters

14.3.5.3 Coagulation Results**Table 33: Coagulation Abnormal Results by Parameter, Dose Group, and Timepoint**

[Parameter order: activated partial thromboplastin time, prothrombin time, international normalized ratio.]

This table will repeat Table 27 for Coagulation Parameters

Table 34: Coagulation Laboratory Toxicity Grade by Parameter, Dose Group, Timepoint, and Severity

[Parameter order: activated partial thromboplastin time, prothrombin time, international normalized ratio.]

This table will repeat Table 28 for Coagulation Parameters

Table 35: Coagulation Summary Statistics Change from Baseline by Parameter, Dose Group, and Timepoint

[Parameter order: activated partial thromboplastin time, prothrombin time, international normalized ratio.]

This table will repeat Table 29 for Coagulation Parameters

14.3.5.4 Urinalysis Results**Table 36: Urinalysis Abnormal Results by Parameter, Dose Group, and Timepoint**

[Parameter order: specific gravity, pH, occult blood, leukocyte esterase, urine RBC, and urine WBC]

This table will repeat Table 27 for Urinalysis Parameters

Table 37: Urinalysis Laboratory Toxicity Grade by Parameter, Dose Group, Timepoint, and Severity

[Parameter order: specific gravity, pH, leukocyte esterase, urine RBC, and urine WBC]

This table will repeat Table 28 for Urinalysis Parameters

Table 38: Urinalysis Summary Statistics Change from Baseline by Parameter, Dose Group, and Timepoint

[Parameter order: specific gravity and pH.]

This table will repeat Table 29 for Urinalysis Parameters (specific gravity and pH only)

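### Urine RBC and WBC percentages in SAP Tables 36 and 37 are conditional on an abnormal dipstick, so they are not comparable across Dose Groups

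*SAP*

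**What the plan says.** **Microscopy is a reflex test.** SAP 4.5 states: "If dipstick urinalysis testing is abnormal, RBC by complete UA and WBC by complete UA will be assessed". Protocol 7.2.1 (Urinalysis) gives the routine panel as "leukocyte esterase, blood, pH, and specific gravity", with "microscopic tests to be completed if dipstick urinalysis is abnormal". Protocol Appendix A (footnote h) and SAP 9.6 repeat the rule. SAP 9.6 adds that microscopy done without an abnormal dipstick will still be summarised.

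**Denominators are set per parameter.** Under SAP 6.1 the denominator at a planned timepoint "will be the number of subjects with available results at the specified timepoint for that parameter". For Maximum Severity Post Baseline it "will be the number of subjects with an observed result for the parameter obtained post dose".

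**The table shells follow that rule.** The footnote to the Table 27 and 28 shells reads "N=Number of subjects in the Safety Population with the laboratory result assessed at the respective timepoint". Table 36 repeats Table 27 for urinalysis and Table 37 repeats Table 28. The parameter list for Table 37 is "specific gravity, pH, leukocyte esterase, urine RBC, and urine WBC". Table 36 has the same five plus dipstick occult blood.

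**Grades.** Protocol Appendix B and SAP Table 4 grade three urine items: protein, glucose and microscopic red cells.

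**Missing data.** SAP 6.5 allows imputation of missing PK collection times and plans no other imputation.

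**The concern.** A missing microscopy result normally means that the dipstick was normal, so it carries information. A denominator made up only of subjects with a microscopy result removes the subjects with normal urine and keeps those already flagged. What remains is the rate of red or white cells given an abnormal dipstick, placed in tables whose other rows are rates among all subjects assessed.

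The row affected is the one that counts most in Table 37. Protein and glucose have grades but are not in the panel. The four dipstick items have no grades, and SAP 4.5 says that urine WBC will not be graded. Of the five parameters listed for Table 37, only urine RBC can carry a Table 4 grade.

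Laboratory tests are part of the primary safety outcome, and these tables exist so that Dose Groups can be read against each other and against pooled placebo. Percentages with differently selected denominators do not allow that comparison.

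**Working it through.** The documents give no dipstick-abnormal rate and no haematuria rate, so there is no planned figure to reproduce. What can be checked is the denominator rule. All event and microscopy counts below are assumptions.

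**Inputs from the documents**
- 6 active and 2 placebo subjects per cohort, six cohorts (SAP Section 2).
- Each active Dose Group therefore has 6 subjects. Pooled Placebo has 2 × 6 = 12 dosing periods and Any Dose has 6 × 6 = 36, because SAP 3.3.2 counts Cohorts 3 and 6 separately.

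**Formula**
- Let T be the subjects with a urinalysis at a timepoint, M those with microscopy, and x those with a graded urine RBC.
- The plan prints x/M. The share of tested subjects is x/T.
- If M = qT and every graded case is among the M, then x/M = (x/T)/q. The printed figure is larger by a factor of 1/q.

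**Numbers**

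| Group (assumed counts) | Printed, x/M | Share of tested, x/T |
|---|---|---|
| Dose Group, 1 case, 3 microscopies | 1/3 = 33% | 1/6 = 17% |
| Dose Group, 1 case, 2 microscopies | 1/2 = 50% | 1/6 = 17% |
| Dose Group, 1 case, 1 microscopy | 1/1 = 100% | 1/6 = 17% |
| Any Dose, 3 cases, 9 microscopies | 3/9 = 33% | 3/36 = 8% |
| Pooled Placebo, 1 case, 3 microscopies | 1/3 = 33% | 1/12 = 8% |

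For assumed q = 0.1, 0.2, 0.3 and 0.5, the factor 1/q is 10, 5, 3.3 and 2. A 5% share among tested subjects would then print, on average, as about 50%, 25%, 17% and 10%.

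**How often N would be very small.** With 6 independent subjects, P(M = 0) = (1 − q)^6, and P(M ≤ 1) = (1 − q)^6 + 6q(1 − q)^5.

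| q | P(M = 0) | P(M ≤ 1) |
|---|---|---|
| 0.1 | 53% | 89% |
| 0.2 | 26% | 66% |
| 0.3 | 12% | 42% |

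At these values a Dose Group would often have no denominator at all, or a denominator of one.

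**Comparison between groups.** Suppose a Dose Group has 2 graded cases from 4 microscopies and Placebo has 1 from 1. The plan prints 50% against 100%. Among tested subjects the figures are 2/6 = 33% against 1/12 = 8%. The order reverses because the two denominators were selected differently.

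**Does anything else in the SAP correct this?** SAP 6.5 does not treat a normal dipstick as absence of haematuria. SAP 9 calls for an Any Parameter row for urinalysis, but its N is not separately defined.

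**The case against.** The strongest reply is that the information is not lost, and most of that reply stands.

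- N is printed beside n (%), and the footnote says that it counts subjects with that result assessed. A reader might infer that the tables pass off a conditional rate as a rate in the whole Safety Population. They do not, because the denominator is disclosed.
- A reader might infer that a urinary signal would be hidden. The documents do not support that. Table 36 reports dipstick occult blood and leukocyte esterase, which belong to the routine panel. Table 26 lists every abnormal urinalysis result, Listing 15 lists all results, and haematuria reported as an AE uses Safety Population denominators (SAP 9.3.2).
- A reader might infer that active and placebo columns would both approach 100%. Microscopy follows any dipstick abnormality, not only one for blood, so many microscopies could show few red cells. SAP 9.6 also lets in microscopy done without an abnormal dipstick. 1/1 is the extreme case.
- Urine RBC is the only collected urine parameter with a Table 4 grade. Other clinically significant urinalysis abnormalities can still be graded as AEs under Protocol 8.5.
- The Any Parameter row in Table 37 would show graded haematuria over all tested subjects if its N were subjects with any urinalysis. That is a natural reading, but the SAP does not state it. If it is meant, the same case would appear in two rows with different percentages and no explanation.

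None of this makes the urine RBC and WBC percentages comparable across groups. The off-plan microscopies make N a mixture, which is harder to interpret.

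**Conclusion.** The point holds, with limited reach. Following the stated rule gives urine RBC and WBC percentages that are conditional on an abnormal dipstick and cannot be compared across Dose Groups. It affects two parameters in Table 36 and one gradable parameter in Table 37, at planned timepoints and in the Maximum Severity row.

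The size depends on how many subjects have microscopy, which the documents do not give. One case among 6 tested subjects, 17%, would print as anything from 33% to 100% with 3 to 1 microscopies. These counts are illustrations and not predictions.

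No hypothesis test or sample size depends on these tables. The halting rules in Protocol 8.6 use SAEs, counts of subjects with AEs and QTcF thresholds. The change is worth making because the rule as written gives misleading percentages in primary safety tables and the data needed to correct it are already collected.

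**What to change.** 1. In SAP 6.1 and the shells for Tables 36 and 37, set N for urine RBC and urine WBC to subjects with any urinalysis (dipstick or microscopy) at the timepoint. For Maximum Severity Post Baseline, use subjects with any post-dose urinalysis.
2. Give the urinalysis Any Parameter row the same N.
3. Count a normal dipstick without microscopy as no graded abnormality, say so in a footnote, and make SAP 6.5 consistent with it.
4. Show the number of subjects with microscopy alongside, so that the conditional figure can still be worked out.
5. In SAP Table 4, mark the urine protein and glucose rows as not collected, or remove them. Reporting those grades instead would assume dipstick readings that the listed panel does not include.

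The cost is one sentence in SAP 6.1, a line in SAP 6.5, table footnotes and a programming rule for two parameters and one summary row. No extra samples or visits are needed. The small downside is that an unperformed microscopy is assumed normal, which is why the footnote and the microscopy count are part of the change. SAP Section 15 already reports Cohort 6 attendance in the past tense; if the SAP can no longer be amended, the same rule can be applied and justified in the CSR as a deviation, as SAP Section 1 provides.

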6.2. Timing of Analyses

The final analysis will be performed after database lock.

An interim PK analysis is planned between Cohort 3 and Cohort 4. Enrollment for Cohort 4 will not depend on the PK interim analysis.

The SMC will review data at the following times:

- Between Cohort 4 and Cohort 5
- After completion of dosing and final visit for all cohorts
- *Ad hoc* meeting(s): as required in response to halting criteria (Protocol section 8.6) being met for sentinels, dose escalation, or the overall study, or at the request of DMID to review a potential safety concern identified by either the PI, medical monitor, participating investigator, or the independent safety monitor (ISM) .

6.3. Analysis Populations

All analysis populations to be used in the final analysis are described in this section. A tabular listing of all randomized and enrolled subjects excluded from an analysis population (Safety Population or a PK Analysis Population) will be included in the CSR ([Listing 5](#)). In the case there are multiple reasons for exclusion from the PK Analysis Population or PK Analysis Subset, only one reason will be counted when summarizing reasons for exclusion from analysis populations in [Table 10](#).

6.3.1. Safety Population

The Safety Population will include all subjects that received any amount of study product and will be analyzed by Dose Group. Placebo subjects will be pooled across multiple cohorts for analysis. Placebo

subjects enrolled in Cohort 3 that continued on to Cohort 6 will be counted separately for each study part, as detailed in Section 3.3.2.

6.3.2. PK Analysis Population

The PK Analysis population will consist of all subjects who received VT-1598 and have at least 1 quantifiable post dose plasma or urine sample with measurable drug or metabolite concentration. Subjects who participated in both Cohort 3 and Cohort 6 will be evaluated and included separately per dosing period for inclusion into the PK Analysis Population; i.e., subjects will be included in the PK Analysis Population once under a Fasted state and once again under a Fed state. Similarly, results from these subjects will be analyzed separately per dosing period. Subjects enrolled and randomized to receive some dose of VT-1598 who did not complete his or her dose, or otherwise received an incorrect dose will not be included in the respective Dose Group for analysis. However, listings will include concentrations and parameter estimates for those subjects. Regardless of the subject's inclusion in the PK Analysis Population, all VT-1598 and VT-11134 concentration results will be included in listings, including results from placebo subjects. The order that reasons will be considered for a PK Analysis Population will be: the subject received placebo, the assigned dose was not received or completed, the subject has no measurable drug or metabolite concentration in plasma or urine.

6.3.2.1. PK Analysis Subset

The PK Analysis Subset will be based on the PK Analysis Population and will include all subjects who completed the PK part of the trial in each dosing period without any protocol deviation that would likely affect the PK results and who have an evaluable plasma or urine concentration for either VT-1598 or VT-11134 from which at least a subset of the designated PK parameters can be determined. The order that reasons will be considered for a PK Analysis Subset will be: excluded from the PK Analysis Population, occurrence of protocol deviation(s) with potential to impact PK, PK data is insufficient to estimate any plasma or urine PK parameters.

